2.0 Objectives

Aim 1 (Phase 1). Refine a treatment protocol for preoperative education and training and postoperative application of VR-BF in children and adolescents undergoing surgery. We will collect qualitative feedback (regarding content, usability, perceived benefits) via questionnaires and a semi-structured interview and sensitivity to change of key physiological parameters (heartrate variability, respiratory rate) from 12-32 patients (12-18 years) undergoing surgery anticipated to cause moderate to severe pain. Purposive sampling will be used to obtain a representative sample of a broad patient population. Treatment protocol refinement using iterative methodology will allow us to define the trial protocol, including frequency and duration of **(1a)** preoperative education and training and **(1b)** postoperative administration of VR-BF.

Feasibility and Acceptability of Technology-Based Interventions in the Perioperative Setting

Aim 2 (Phase 2). Conduct a pilot randomized controlled trial to assess the feasibility and acceptability of perioperative use of VR-BF in children and adolescents undergoing surgery. Seventy children and adolescents (12-18 years) scheduled for surgeries anticipated to cause moderate to severe pain will be randomized to receive VR-BF or active control (commercially available *Manage My Pain* application). *Manage My Pain* is engaging but lacks specific instruction in behavior change techniques, a key feature of VR-BF. It is included as the control arm to confirm appropriateness for use in the future efficacy trial. Specifically, (2a) Feasibility will be assessed by rates of study recruitment, enrollment and randomization, retention, and adherence. Target goals will be set at 80% for each assessment. (2b) Acceptability will be assessed by treatment/study burden, satisfaction, treatment credibility, and tolerability. It is essential that both treatment arms are feasible and acceptable for use in an efficacy trial.

Our central hypothesis is that preoperative education and training combined with independent, self-directed, repeated postoperative use of VR-BF will be feasible and acceptable in this population. This proposal addresses key components necessary for the design of a large-scale, clinical efficacy trial.

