Data Collection (Table 3). **Feasibility.** *Recruitment:* The number of patients screened per month will be recorded and assessed for eligibility; reasons for ineligibility will be recorded. If 80% of patients do not meet criteria, we will adjust criteria as necessary. *Enrollment and randomization:* Enrollment and randomization will be defined as agreeing to participate in the study and being willing to be randomized. We will record the number of eligible patients approached and enrolled each month. We will collect reasons for refusal to enroll, including unwillingness to be randomized. If rates are not maintained at 80%, we will adjust strategies accordingly. *Retention:* We will define retention as the number of patients who complete the study by participation in the last study visit for both arms. We will collect reasons for dropout. If $\geq 80\%$ retention is not maintained, we will evaluate reasons for dropout. *Adherence:* We will define adherence to preoperative training as completion of the education and training session with the study team and completion of $\geq 5/7$ daily sessions. Adherence to postoperative VR-BF/app use will be defined as completion of $\geq 5/7$ daily sessions. Our target will be $\geq 80\%$ completion. We will collect reasons for failure.

Questionnaires and the semi-structured interview will also assess feasibility using measures based in the literature.¹¹⁹

Acceptability. Treatment/Study

Burden: Burden will be assessed by collecting data on daily log completion, data from questionnaires, and participation in the interview. We will collect reasons for drop out to better understand treatment and study burden.

	Measures	Definition	Benchmarks	Additional Data
Feasibility	Recruitment	Number of patients screened per month	$\geq 80\%$ will meet eligibility criteria	Reasons for not meeting criteria
	Enrollment and randomization	Number of patients approached who agree to enroll in the study and be randomized to a treatment arm	$\geq 80\%$ of those approached will agree to enroll and be randomized	Reasons for refusal, including unwillingness to be randomized
	Retention	Number of participants who complete the study as defined by participation in the last study visit	$\geq 80\%$ retention	Reasons for dropout
	Adherence	Treatment-specific adherence	$\geq 80\%$ will complete ≥ 1 session per day for $\geq 5/7$ days (preop) and ≥ 1 session per day (postop)	Reasons for failure

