Quantitative analysis (dose). Data will be collected on number of daily practice (preoperative) and therapy (postoperative) sessions completed by each patient, duration of each session, and changes in HRV and respiratory rate parameters over time. We will also assess the total daily dose of sessions by totaling the duration of all sessions per day and assessing the mean and variability of the daily dose. These quantitative data together with quantitative responses from the questionnaires and interviews will be summarized using frequency and percent for categorical variables and mean \pm SD or median and IQR for continuous variables. For variables measured multiple times per participant (duration of each practice/therapy session, changes in HRV and respiratory rate), within- and between-subject summary measures of location and variability will be derived and examined.

Sample size. No statistical power analysis was done to determine the sample size for Aim 1. Rather, sample size determination was based on our extensive pilot work and clinical experience with the population along with the team's expertise in protocol refinement studies in intervention development.

Anticipated outcomes. At the end of Phase 1, we anticipate having a refined treatment protocol for preoperative education and training, and postoperative application of VR-BF. This protocol will be piloted in Phase 2. Results from Aim 1 will provide a preliminary study protocol and manual of procedures for the clinical efficacy trial that will be finalized at the end of Aim 2.

Feasibility and Acceptability of Technology-Based Interventions in the Perioperative Setting

Aim 2:

Data analysis. Phase 2 is a single-center, randomized, two-arm, parallel-group, single blinded trial to assess the feasibility and acceptability of the treatment protocol designed in Aim 1. We will ensure study transparency, describing recruitment, enrollment, and outcomes in a Consolidated Standards of Reporting Trials (CONSORT) diagram^{106,120} and provide detailed descriptions of the intervention and active control. Demographic and baseline characteristics will be summarized for all patients and within each study group (categorical variables: frequency and percent; continuous variables: mean \pm SD or median and IQR).

Quantitative analysis. We will assess measures of feasibility and acceptability for each arm.

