Feasibility. We will calculate descriptive data on 1) How many patients are screened per month; 2) Percentage of patients meeting eligibility criteria; 3) Percentage of eligible patients approached, enrolled, and randomized; 4) Percentage of patients completing Phase 2; and 5) Percentage of patients adhering to preoperative education and postoperative application of VR-BF as defined in the study measures. For each measure, the rates, variances, and two-sided 95% confidence interval (CI) will be reported. Each CI will be examined to determine if the hypothesized value of 80% is contained within the interval. This data will also be used to generate a diagram of participant flow. Because this is a feasibility study, we will not conduct statistical tests on the clinical outcomes collected for exploratory purposes (pain and anxiety ratings, opioid use). We will analyze this data using descriptive measures stratified by treatment arm. **Acceptability.** We will calculate descriptive data on 1) Treatment/study burden: number and percentage of patients completing all study measures; 2) Tolerability: number and percentage of patients experiencing AEs; and 3) Any quantitative data of satisfaction and treatment credibility from questionnaires and semi-structured interviews. For each of these measures, the rates, variances, and two-sided 95% CI will be reported. The CI for treatment/study burden will be examined to determine if the hypothesized value of 80% is contained within the interval. Qualitative treatment credibility and parent/patient satisfaction data will be assessed qualitatively as described below.

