Qualitative analysis. From the questionnaires and semi-structured interviews, we will compile data on satisfaction, credibility, and tolerability as well as additional feasibility data. This qualitative data will be analyzed in the same way as in Aim 1.

Sample size. Seventy subjects will be enrolled and randomized to one of two study arms: intervention and active control. As this is a pilot feasibility and acceptability study, no confirmatory hypothesis testing will be done. Our sample size is based on estimation of two-sided CIs for one proportion with exact formula of the binomial probabilities. To estimate a 95% CI with targeted width of 0.22 and an assumed proportion of 80%, we will need a sample size of 70 (35 per group), resulting in a total of 56 patients (28 per group) included in the analysis after 80% retention.

Anticipated outcomes. We anticipate creating a final VR-BF study manual that will define study procedures for an efficacy trial and provide key pilot data for future grant applications. By the end of Phase 2, we expect to have 1) A defined patient population with clearly delineated eligibility criteria; 2) A clearly delineated preoperative education and training protocol for VR-BF/active control; 3) A dosing strategy (frequency, duration) for postoperative administration of VR-BF/active control; 4) Feasibility and acceptability data for VR-BF/active control; and 5) A preliminary assessment of key outcome measures (pain, anxiety, opioid consumption) to be evaluated in the efficacy trial.

Data Safety:

Data confidentiality will be maintained by data being stored in a password protected computer and any hard copies of patient information stored in a locked office. Data will be transmitted to a password-protected Nationwide Children's computer for further analysis. Data held in REDCap is deemed secure. All individuals using and interacting with this data will be trained appropriately and a member of the study team. Any data transmission will occur via secure emails (not personal). Proper agreements have been executed to cover the sharing of de-identified data from REDCap with a statistician at CCHMC. Data will be de-identified by selecting the option to export data directly from REDCap with all known identifier fields (date, name, address, MRN, etc.) removed. The exported data set will then be shared with CCHMC. Data will be stored for the duration of the study and analysis/presentation up to the time period specified by the IRB.

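### The 0.22 confidence interval width that justifies N = 70 holds only for both arms pooled after dropout; within an arm it is about 0.285 to 0.32, and the plan does not say so

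*Combined protocol and SAP*

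**What the plan says.** All references are to the combined protocol and SAP.

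- **Section 17.0, Aim 2, Sample size.** The calculation uses a two-sided exact binomial interval for one proportion: "To estimate a 95% CI with targeted width of 0.22 and an assumed proportion of 80%, we will need a sample size of 70", that is 35 per group, "resulting in a total of 56 patients (28 per group) included in the analysis after 80% retention". The text does not say whether 0.22 refers to the pooled sample or to one arm. It is the only precision statement for the randomized phase.
- **Section 17.0, Aim 2, Quantitative analysis.** "We will assess measures of feasibility and acceptability for each arm".
- **Section 2.0, Aim 2.** "It is essential that both treatment arms are feasible and acceptable for use in an efficacy trial".
- **Section 17.0, Aim 2, Feasibility.** Rates are reported with 95% intervals, and "Each CI will be examined to determine if the hypothesized value of 80% is contained within the interval". The Acceptability text repeats this for burden: "The CI for treatment/study burden will be examined to determine if the hypothesized value of 80% is contained within the interval".
- **Section 6.0, Data Collection and Table 3.** The benchmarks are observed rates of at least 80%. For retention, "We will define retention as the number of patients who complete the study by participation in the last study visit for both arms"; if the 80% level of "retention is not maintained, we will evaluate reasons for dropout". Table 3 sets the same 80% level for adherence and burden.

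**The concern.** The stated width and the planned analysis sit at different levels. The objective rests on what is learned about each arm, but 0.22 describes the two arms combined. Because the per-group counts are printed beside 0.22, a reader could easily take it as the per-arm width.

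Two further points follow:

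- **Denominators.** The 56 are by definition the patients who were retained, so retention must be computed on those randomized. For adherence and burden, the plan does not say whether the denominator is all randomized patients or completers.
- **Reading the intervals.** With intervals this wide, an arm can fall well short of 80% while its interval still contains 80%. The plan gives both an interval check and an observed-rate benchmark, and does not say that passing the first is no evidence of meeting the second.

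The results are meant to inform the design of an efficacy trial, so an over-favourable reading of either arm would carry forward.

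**Working it through.** **Inputs.** From Section 17.0, Aim 2, Sample size: two-sided 95% exact interval, proportion 0.80, target width 0.22, 70 randomized (35 per group), 80% retention, 56 analysed (28 per group).

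**Formula.** For x successes in n, the exact (Clopper-Pearson) limits are

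- lower = Beta quantile at 0.025 with parameters (x, n − x + 1)
- upper = Beta quantile at 0.975 with parameters (x + 1, n − x)

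and width = upper − lower. Where 0.8n is not a whole number, the width at 0.8n is given first and the attainable counts beside it.

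**Step 1: reproduce the plan's figure.** 70 × 0.80 = 56. At n = 56 and 80% the interval is 67.2% to 89.5%, width 0.223. The mean width over Binomial(56, 0.8) is 0.2205. Both round to 0.22, so the stated figure is the pooled, post-dropout width.

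**Step 2: the same formula at the other sample sizes.**

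| Sample | n | Count | 95% exact CI | Width |
|---|---|---|---|---|
| Pooled, randomized | 70 | 56 | 68.7% to 88.6% | 0.199 |
| Pooled, after dropout | 56 | 44.8 | 67.2% to 89.5% | 0.223 |
| One arm, randomized | 35 | 28 | 63.1% to 91.6% | 0.285 |
| One arm, after dropout | 28 | 22.4 | 60.7% to 92.6% | 0.320 |
| One arm, after dropout | 28 | 22 | 59.1% to 91.7% | 0.327 |
| One arm, after dropout | 28 | 23 | 63.1% to 93.9% | 0.308 |

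Relative to the pooled width: 0.285 / 0.223 = 1.28 and 0.320 / 0.223 = 1.43. Other interval methods do not bring one arm to 0.22: at n = 35 the Wald width is 0.265 and the Wilson width 0.258; at n = 28 they are 0.296 and 0.287.

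**Step 3: retention.** Its denominator is the randomized patients, so the relevant widths are 0.285 per arm and 0.199 pooled. The stated 0.22 is neither.

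**Step 4: the interval check against the benchmark.** All counts whose exact interval contains 80% were listed and compared with the smallest count that gives an observed rate of at least 80%.

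| n | Interval contains 80% | Smallest count at or above 80% | Contains 80% but misses benchmark |
|---|---|---|---|
| 28 | 18 to 26 | 23 | 18 to 22 (64% to 79%) |
| 35 | 23 to 32 | 28 | 23 to 27 (66% to 77%) |
| 56 | 39 to 50 | 45 | 39 to 44 (70% to 79%) |

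For example, 18/28 has the interval 44.1% to 81.4%. The first counts that exclude 80% from below are 17/28 (upper limit 78.5%), 22/35 (78.5%) and 38/56 (79.7%).

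**Step 5: how often the two readings differ.** The documents give no true rate below 80%, so 65% is assumed here, with 60% to 70% as a range. The chance is the Binomial(n, p) sum over the last column of the Step 4 table.

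| n | True rate 65% | True rate 60% to 70% | Observed rate ≥ 80% when true rate is 65% |
|---|---|---|---|
| 28 | 58% | 39% to 70% | 4% |
| 35 | 50% | 30% to 64% | 4% |
| 56 | 27% | 9% to 53% | 1% |

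**The case against.** The strongest reply is that nothing here is miscalculated. The method, the assumed proportion, the width and the per-group counts are all printed, so a reader could derive the per-arm width. The phase is a pilot with no confirmatory testing. That is correct, and it is why N = 70 is not challenged. It does not remove the mismatch: the plan chose a precision criterion and a level of analysis, and the one is not delivered at the other.

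A second reply is that the plan only says the intervals will be examined. It never says that containing 80% means success, and its responses are tied to observed rates. This also stands in part: the observed-rate benchmark governs, and the percentages in Step 5 are not error rates of any decision rule in the plan. They show only how little the interval check tells you within an arm.

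Third, Section 6.0 also anticipates that at least 75% of patients will complete all study measures. Judged against 75%, 21/28 and 22/28 would pass for burden. But that figure is an expectation, and the benchmark in Table 3 is 80%.

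Finally, pooled retention on 70 patients has width 0.199, so 0.22 is conservative there. Eligibility and enrollment rates precede randomization and have no per-arm version. Both limits are accepted: the point concerns the arm-level measures of retention, adherence and burden.

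**Conclusion.** The concern holds, as a minor one. The 0.22 is right for 56 pooled patients and for nothing else the plan estimates by arm. At an observed rate near 80%, the per-arm width is 0.285 with 35 patients and about 0.32 with 28 (0.308 to 0.327 at the attainable counts). The only stated precision is therefore more favourable than the per-arm estimates on which the objective depends.

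The widths rest on the plan's own method, proportion and retention. Which of the two per-arm widths applies to adherence and burden depends on a denominator that the plan leaves open. Only the Step 5 chances need an outside assumption, the true rate of 60% to 70%. The effect is on how the per-arm intervals are read, not on enrollment or a go/no-go decision.

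**What to change.** Keep N = 70 and make these wording changes in Section 17.0, Aim 2.

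1. **Sample size.** Replace the precision statement with wording such as: *Pooled over 56 analysed patients, the exact 95% CI at an observed 80% has width about 0.22; per arm, at an observed rate near 80%, the width is about 0.32 with 28 patients and about 0.285 with 35.*
2. **Feasibility and Acceptability.** State that retention uses all randomized patients (35 per arm), and name the denominator for adherence and for burden: all randomized or completers.
3. **Same paragraph.** State that a per-arm interval containing 80% is not by itself evidence that the 80% benchmark in Section 6.0 and Table 3 was met.

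The cost is two or three sentences and a less favourable stated precision per arm. No extra patients, visits or data are needed. A larger trial would be required only if the sponsor wanted a width of about 0.22 within each arm: 56 to 58 analysed per arm, so 112 to 116 in total, or about 140 to 145 randomized at 80% retention (112 / 0.8 = 140; 116 / 0.8 = 145). That is not recommended here.

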After surgery, as in Aim 1, a trained CRC will visit patients daily or as needed while hospitalized. Control group patients will complete a daily application-generated usage report (date, time, duration); VR-BF patients will have this information, along with HRV and respiratory rate data, obtained from the device. To help determine what outcomes may be impacted by VR-BF for future trial development, patients will also be asked to document pain and anxiety scores before and after each VR-BF or application session using the NRS.^{110,111} Patients will self-report and document these scores before each session and then immediately, 15 minutes, and 30 minutes after session completion. All pain scores and opioid consumption (in morphine equivalents mg/kg/day) will be collected from EPIC, the electronic medical record, for each 24-hour period during study enrollment; anxiety scores are not documented by the nursing staff so only self-reported scores will be used. Documented pain scores will also help finalize the “dose” of VR-BF to be used in the efficacy trial as we will assess for correlation, if any, between pain score and use of VR-BF. At the final study visit prior to discharge, patients will answer a questionnaire and engage in a semi-structured interview soliciting qualitative feedback about their experience with the intervention or control to finalize the study protocol for the clinical efficacy trial. Participants will be given the option to take the VR-BF platform home or continue using the *Manage My Pain* application for up to two weeks after discharge. If this option is selected, patients will complete a daily log/report documenting use, pain scores, and opioid consumption. During the first postoperative clinic visit, VR-BF and reports/logs will be collected and questions about home use will be asked, answered, and recorded. Parents will also be asked to complete a survey about their experience and opinions. If patients cannot be met during the first postoperative clinic visits, other arrangements will be made to collect the information and equipment.

Feasibility and Acceptability of Technology-Based Interventions in the Perioperative Setting

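### The planned interval width of 0.22 holds only for about 56 retained patients pooled over both arms, while measures are assessed per arm and adherence and burden have no stated denominator

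*Combined protocol and SAP*

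**What the plan says.** Section 17.0 (Aim 2, Sample size) bases the sample size on an exact binomial two-sided 95% interval for one proportion, with target width 0.22 at an assumed 80%. It enrols 70 patients (35 per group), "resulting in a total of 56 patients (28 per group) included in the analysis after 80% retention".

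Section 17.0 (Aim 2, Quantitative analysis) says that feasibility and acceptability are assessed for each arm. Section 2.0 says that both arms must prove feasible and acceptable.

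The measures at issue are in section 17.0 (Feasibility and Acceptability). Adherence is the "Percentage of patients adhering to preoperative education and postoperative application of VR-BF as defined in the study measures". Burden is the "number and percentage of patients completing all study measures". Each gets a 95% interval, which is examined to see whether it contains 80%. The same feasibility list includes "Percentage of patients completing Phase 2".

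Section 6.0 (Data Collection) states: "We will define retention as the number of patients who complete the study by participation in the last study visit for both arms". It links dropout to burden: "We will collect reasons for drop out to better understand treatment and study burden". It defines preoperative adherence as the training session plus at least 5 of 7 daily sessions. For postoperative adherence, the text requires at least 5 of 7 daily sessions, while Table 3 requires at least one session per day.

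**The concern.** Two things follow from one planning sentence. First, the stated precision describes a pooled rate, but the question the trial asks is answered arm by arm. A reader who takes 0.22 as the precision of each arm's result will expect intervals much narrower than the trial can give.

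Second, no section names the denominator for adherence or burden, and the only analysed number in the plan is the retained 56. A patient who leaves because the headset or application is too demanding bears directly on both measures, yet would vanish from them on a retained-only base. If dropout differs between arms, the two arms would be affected by different amounts. Two analysts following the text could report different rates from the same data, and those rates inform the design of the efficacy trial.

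**Working it through.** **Inputs.** From section 17.0: exact two-sided 95% interval, assumed rate 80%, target width 0.22, 70 enrolled (35 per arm), 56 analysed (28 per arm) at 80% retention, and comparison of each interval with 80%. How many dropouts met a definition before leaving is not in the documents, so it is varied over its full range.

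**Formula.** For x successes in n, the exact (Clopper-Pearson) limits are the 2.5% quantile of Beta(x, n − x + 1) and the 97.5% quantile of Beta(x + 1, n − x).

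**Step 1: the plan's own figure.** With x = 0.8n treated as continuous:

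| n | Exact interval | Width |
|---|---|---|
| 56 (retained, pooled) | 0.672 to 0.895 | 0.223 |
| 70 (randomized, pooled) | 0.687 to 0.886 | 0.199 |
| 28 (retained, per arm) | 0.607 to 0.926 | 0.320 |
| 35 (randomized, per arm) | 0.631 to 0.916 | 0.285 |

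The plan's figure reproduces at n = 56, and 56/0.80 = 70. Per arm, the width is 0.320/0.22 = 1.45 times the stated value with 28 patients and 0.285/0.22 = 1.30 times with 35.

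**Step 2: the denominator.** The percentage completing Phase 2 must be taken over all randomized patients, since among completers it would be 100%. Adherence is the next item in that list and could be read the same way, or on the 56. If no dropout met the definition, a rate r among the retained becomes 0.8r among the randomized, so 80% becomes 64%. If some did, the shift is smaller.

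**Step 3: the check per arm.** With 28 of 35 retained there are 7 dropouts. The interval contains 80% for 18 to 26 successes out of 28, and for 23 to 32 out of 35. For c successes among the retained and k among the dropouts, compare c/28 with (c + k)/35:

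| c of 28 | Interval on 28 | Against 80% | c + k of 35 | Result differs on 35 when k is |
|---|---|---|---|---|
| 21 | 55.1% to 89.3% | contains | 21 to 28 | 0 or 1 |
| 22 | 59.0% to 91.7% | contains | 22 to 29 | 0 |
| 23 to 25 | 63.1% to 93.9% (23), 71.8% to 97.7% (25) | contains | 23 to 32 | never |
| 26 | 76.5% to 99.1% | contains | 26 to 33 | 7 |
| 27 | 81.7% to 99.9% | above | 27 to 34 | 0 to 5 |
| 28 | 87.7% to 100% | above | 28 to 35 | 0 to 4 |

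For example, 22/35 = 62.9% (44.9% to 78.5%) lies below 80%. At the top, 27/35 (59.9% to 89.6%) and 28/35 (63.1% to 91.6%) contain 80%.

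**Step 4: the check pooled.** 45/56 = 80.4% (67.6% to 89.8%) contains 80%; 45/70 = 64.3% (51.9% to 75.4%) does not. With 14 dropouts, and 49 to 62 of 70 containing 80%, the result differs only while 45 + k ≤ 48, that is, with 0 to 3 adherent dropouts. If all 14 adhered, the rate is 59/70 = 84.3% (73.6% to 91.9%).

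**Step 5: where in that range dropouts may fall.** Section 6.0 places the patient questionnaire and interview before discharge ("At the final study visit prior to discharge, patients will answer a questionnaire and engage in a semi-structured interview") and a further contact later ("During the first postoperative clinic visit, VR-BF and reports/logs will be collected and questions about home use will be asked, answered, and recorded"). If the later contact is the visit that defines retention, a patient lost between the two may already have met a definition. A patient lost after surgery also has complete preoperative adherence data. Counting every dropout as a failure is therefore one end of the range.

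**The case against.** The strongest reply is that the 56 sits in a sample-size sentence and is not an analysis set. That is correct. A reader might infer that the plan prescribes a completers-only analysis of adherence and burden. The documents do not say so, and collecting dropout reasons under burden points, if anything, the other way. What stands is that no other text settles the base.

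A second reply is that the pooled contrast of 45/56 with 45/70 exaggerates the effect, because measures are assessed per arm. This also stands. Near the planned rate (22 or 23 of 28), the per-arm check changes only at 22, and then only if none of the 7 dropouts met the definition.

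Third, dropout is not hidden: retention has its own rate and interval, reasons are collected, and a CONSORT diagram is planned. With counts reported, a reader could bound most of the effect. This limits the harm but does not make the base unambiguous.

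Fourth, retention is measured separately from adherence and burden, so counting leavers as failures partly merges them. That is a fair cost of the proposed denominator and a reason to show both versions. None of these replies touches the mismatch between the pooled width and the per-arm assessment.

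**Conclusion.** The precision statement needs correction: 0.22 describes about 56 pooled patients, and each arm will have an interval about 0.32 wide (28 patients) or 0.285 wide (35 patients) at 80%. This rests only on the plan's own method and assumed rate. It does not show that 70 patients is the wrong number; the calculation reproduces for the pooled case.

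The denominator gap is real but conditional. If the retained base is used, and if dropouts met the definitions less often than retained patients, both rates are too high, by up to 16 percentage points at a retained rate of 80% (80% against 64%). A reader might infer that the choice generally reverses the comparison with 80%. It does not: per arm, nothing changes at 23 to 25 of 28, and elsewhere the result depends on how many dropouts met the definition. These figures assume exactly 80% retention in each arm.

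No confirmatory test is planned and no go/no-go rule is tied to the check. Severity is low to moderate: worth correcting before analysis, but not a threat to the trial.

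**What to change.** In section 17.0 (Aim 2, Sample size), restate precision per arm: exact width at 80% of about 0.285 for 35 randomized and 0.32 for 28 retained, with 0.20 for 70 pooled and 0.22 labelled as the pooled retained figure.

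In section 17.0 (Feasibility, Acceptability and Sample size), name all randomized patients in each arm as the main denominator for adherence and burden. Report preoperative and postoperative adherence separately. Credit patients who met a definition before leaving, count those who left without meeting it as not meeting it, and show retained-only rates alongside.

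In section 6.0, reconcile the two postoperative adherence definitions (text and Table 3), since the counting rule cannot be applied until there is one.

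The cost is wording only; no extra patients or data are needed. The downsides are that rates will usually be lower, that patients lost for unrelated reasons count as failures, and that burden will overlap with retention. If no dropout completes all measures, burden cannot exceed the retention rate, so at 80% retention it reaches 28/35 = 80% only if every retained patient completes everything. Showing both bases keeps this visible.
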